systematic review published by the *International Dysphagia Diet Standardisation Initiative* (IDDSI) in 2015 concluded, “**there is a need to classify food and fluid behavior in the context of the physiological processes involved in oral transport and flow initiation**”^[23]. In this project, we are addressing this challenge with a pivotal and comprehensive study **to determine physiological-rheological correlates (i.e. bolus flow and swallowing kinematics) across a continuum of consistencies in healthy and disordered swallowing**. To do this, we will prepare starch- and gum-thickened liquids in 5 consistencies (*Level 0 - thin, Level 1 - slightly-thick, Level 2 - mildly-thick, Level 3 - moderately-thick and Level 4 - extremely-thick*) according to the IDDSI framework. Additionally, we will study physiological correlates of bolus movement with three levels of food texture: *Level 5 – minced & moist, Level 6 – soft & bite-sized and Level 7 – regular*. Operational definitions for these consistencies have been developed by IDDSI based on validated low-technology tests that can be performed by caregivers to verify consistency during meal preparation and at the point of meal delivery (<https://iddsi.org/framework/food-testing-methods/>). Liquid flow is tested using the IDDSI Flow Test, which classifies consistency based on gravity-flow through a standard syringe (<https://iddsi.org/framework/drink-testing-methods/>). Previous phases of this grant have involved the development and characterization of liquid stimuli using the IDDSI Flow Test as well as validation of the testing method. IDDSI tests of solid food characteristics include measurements of particle size, hardness and stickiness/ cohesiveness. In experiments 2, 4, 5, and 6 of this project, we will collect videofluoroscopic and physiological measures of bolus flow and swallowing behavior across a range of liquid consistencies, across different commercial barium products and across foods of different consistency.

4. Methods

Participants:

Experiments 2 and 4 will involve the participation of a single sample of participants in the following sub-groups:

- i) 40 healthy adults, aged under 60 years old, recruited from the Toronto population at large (already complete);
- ii) 40 healthy adults, aged over 60 years old, recruited from the Toronto population at large (90% complete);

Experiment 6 will involve the participation of another sample of participants:

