- i) 20 healthy adults, aged under 60 years old, recruited from the Toronto population at large.

Participants will participate in only one of the two samples (Experiments 2&4 or Experiment 6) . Recruitment for Experiment 4 was terminated on July 24 2018 due to technical issues

encountered with the equipment that could not be repaired by the manufacturer. We will recruit an equal number of male and female participants within each age-group. Participants of all ethnic and racial groups will be accepted, however adequate comprehension of the English language consent documents will be required.

The target age ranges for the age sub-groups have been selected based on our previous research, which suggests that significant age-related differences in tongue pressures in swallowing are detectable over the age of 60^[24-27]. Experiment 6 only includes healthy adults under 60 years of age at this time as this preliminary study exploring barium products/concentration and solids. The results will inform our decision to run a similar study in healthy older adults in the future.

Exclusion Criteria:

- The healthy adult participants for Experiments 2, 4, and 6 will be accepted into the study, provided that they have no prior history of swallowing, motor speech, gastro-esophageal or neurological difficulties, chronic sinusitis or taste disturbance.
- Individuals with a history of surgery to the speech or swallowing apparatus (other than routine tonsillectomy or adenoidectomy) will be excluded.
- Similarly, due to the requirement to swallow stimuli containing a significant carbohydrate load, individuals with Type 1 Diabetes will be excluded.
- For experiment 6, individuals who wear dentures will be excluded.
- Due to the fact that neurological impairments comprise an exclusion criterion, individuals with cognitive communication difficulties that may hinder comprehension of the study documents will be excluded from this study.
- For experiment 6, individuals with known allergies to medical adhesive will be excluded.
- Individuals with known allergies to ingredients of the food and liquid products used in the experiment will be excluded.
- As a further precaution due to the use of radiation in experiments 2 and 6, we will exclude women who report current pregnancy and individuals who report that they have had an x-ray to the neck in the past 6 months.

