We will model the impact of bolus consistency on measures of chewing and videofluoroscopic measures of pharyngeal bolus flow (i.e., the interval from the bolus passing the mandibular ramus until laryngeal vestibule closure; pharyngeal transit time) and pixel-based measures of post-swallow residue. The analysis will involve linear mixed model ANOVAs with repeated measures. A stepwise analysis approach will be used, first identifying relevant influences of tongue-pressure and nasal airflow patterns across stimuli. The influence of variations in bolus volume will also be explored using univariate tests, and, if confirmed to be significant, will be used as a covariate in the subsequent statistical models. Similarly, differences in the dependent variables as a function of sex or age (continuous or divided into groups) will be explored first in a univariate fashion, and, if significant, these between-participant factors will be included in the model.

For Experiment 2, **our main hypothesis is that liquids with similar gravity-flow properties will show similar pharyngeal bolus flow.** Our goal will be to detect differences in bolus flow measures ≥ 200 ms as a function of consistency, with a medium effect size (Cohen's $d \geq 0.5$)⁽⁹⁶⁾. We hypothesize that the healthy participants in these experiments will use higher amplitudes of tongue pressure and/or submental muscle contraction (sEMG) during oral propulsion of starch-thickened stimuli, thereby achieving a similar outcome for both starch- and gum-thickened liquids in terms of pharyngeal bolus flow. Model fit for different covariance structures will be explored using restricted log likelihood estimation. Age-group (< vs. > 60 years) will be used as a between-groups factor while bolus consistency will be used as the within-participants factor. Sample size calculations have been performed using the data from the PI's previous grant, in which ultrasound measures of the duration of hyoid movement differed by 200-400 ms between age-groups and tongue-pressure amplitudes varied by 10-35 mm Hg depending on the liquid studied. A power calculation shows that 36 participants per group will be needed to

detect this difference with 80% power ($\alpha=0.05$). Allowing a margin for attrition, we have therefore planned to enroll $n=40$ per participant group: total $N=80$ for Experiments 2 and 4. This sample size will also be adequately powered for Experiment 4 to detect differences ≥ 10 mm Hg in tongue-pressure amplitudes.

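### Experiment 2 has two unreconciled rules for age in the model, and sex enters only if a univariate test is significant

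*Combined protocol and SAP*

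**What the plan says.** Two places in 4. Methods, Data Analysis, deal with age.

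- **General opening paragraph.** It says that "differences in the dependent variables as a function of sex or age (continuous or divided into groups) will be explored first in a univariate fashion". The rule that follows is that "if significant, these between-participant factors will be included in the model". The significance level for this screen is not given, and the coding of age is left open.
- **Experiment 2 paragraph.** "Age-group (< vs. > 60 years) will be used as a between-groups factor", with bolus consistency as the within-participants factor. There is no condition, and the coding is fixed.

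Sex appears only in the conditional rule. Yet 4. Methods, Participants, treats both variables as recruitment factors: 40 adults under 60 and 40 over 60 for Experiments 2 and 4, and "We will recruit an equal number of male and female participants within each age-group".

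**The concern.** An analyst cannot follow both age rules when age is not significant in the screen, or when continuous age is significant and grouped age is not. No sentence ranks one rule above the other.

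A univariate main-effect test is also a poor gate for a factor the sample was built on. Age groups can respond differently to consistency while their overall means agree; the gate would then usually remove age before that difference is examined. Because the rule applies to the dependent variables generally, and Data Processing lists 19 parameters (a to s) across the experiments, the fitted model could differ from one outcome to the next. At stake are the between-group comparison, any age-by-consistency difference, and the ability to say that the model was fixed before the results were seen.

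**Working it through.** **The plan's own figure.** The plan states 36 per group for 80% power at alpha 0.05, and enrols 40. It gives no SD, test or correlation, so 36 can be neither confirmed nor called wrong. At d=0.5, a two-sided two-sample t-test needs 64 per group and a paired t-test needs 34 participants. In a two-sample test, 36 per group corresponds to d of about 0.67. The point made here does not dispute the 36; d=0.67 is used below only as one plausible value for age.

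**Chance that a true age effect fails the screen.** Inputs: 40 per group (Participants); two-sided 0.05 and one value per participant (assumed); d assumed, because the plan attaches d ≥ 0.5 to differences by consistency, not by age. The noncentrality is δ = d × √(n/2) = d × √20 = 4.472d. The screen fails when |t| < 1.991 on 78 degrees of freedom.

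| d (assumed) | δ | Fails screen |
|---|---|---|
| 0.3 | 1.34 | 74% |
| 0.5 | 2.24 | 40% |
| 0.67 | 3.00 | 16% |
| 0.8 | 3.58 | 6% |

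If the groups differ only in their response to consistency and their overall means are equal, the main-effect test is a null test, and it removes age in 1 − 0.05 = 95% of studies.

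**Two codings of age.** Suppose there is no age effect and the analyst tries both grouped and continuous age, accepting either. Simulations of 20,000 studies with 40+40 participants admit age in about 7% to 7.6% of studies instead of 5%. Ages were assumed uniform, over 20–59 and 61–85 or over 18–60 and 60–85; the two codings correlate at about 0.86 to 0.88.

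**Omitting sex.** Sex is left out only when its test is not significant. With 80 participants that requires an observed R² below t²/(t² + 78) = 1.991²/(1.991² + 78) = 0.048. With sex balanced within age-group, leaving it out inflates the SE of the age contrast by at most about 1/√(1 − 0.048) = 1.025. After allowing for the degree of freedom saved, this is 1.025 × √(77/78) = 1.02. (If age itself explains variance, the 1.025 rises slightly, to about 1.03 at d=0.8.) Simulating a sex effect that explains 10% of variance (assumed; 20,000 runs), sex was dropped in about 16% of studies. The mean SE inflation was 0.9% when it was dropped and 0.14% over all studies. Because of the balance, omitting sex does not bias the age contrast.

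**The case against.** The strongest reply is that the specific rule governs. The paragraph that begins with Experiment 2 fixes both the role and the coding of age. The general paragraph also covers chewing measures, and chewing tasks are described only for Experiment 6. That experiment enrols only adults under 60, so a split at 60 is impossible there and continuous age would have a use. This is a natural reading, and under it age-group cannot drop out of Experiment 2.

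It does not settle the matter. The plan never says that the specific rule overrides the general one. The Experiment 6 paragraph has its own list of screened participant factors, which includes sex but not age. Experiment 4 was terminated. The general age rule is therefore left with little to govern other than Experiment 2. Sex is gated under either reading.

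Three other parts of the reply stand. The main Experiment 2 hypothesis is a within-participant one, and dropping age or sex from near-balanced data hardly moves the average consistency contrast. The plan states no age-by-consistency hypothesis. And it does not say that both codings will be tried and either accepted, so the 7% to 7.6% figure describes what the wording permits, not what is announced.

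**Conclusion.** The point holds as a modest defect of specification. The two age rules are unreconciled, the coding and screening threshold are open under one of them, and sex is admitted by p-value although it was balanced by recruitment. The consequence for age depends on which rule prevails. If it is the general one, the chance of losing a true age effect runs from about 74% (d=0.3) to 6% (d=0.8), assuming a two-sided 0.05 participant-level test.

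Three stronger readings might be inferred, and the documents do not support them:

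- **Age will drop out in 4 studies of 10.** That is the d=0.5 point on a wide range. It borrows an effect size stated for consistency, and it applies only if the general rule governs Experiment 2.
- **Omitting sex costs about 5% in precision.** If sex explained 10% of variance and were always omitted, the SE would grow by 1/√0.9 = 1.054. Under this gate, sex is omitted only when its observed effect is small, so the inflation is at most about 2.5% and usually under 1%.
- **The main hypothesis is compromised.** It rests on a within-participant contrast that is hardly affected.

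**What to change.** State one rule for Experiment 2 in Data Analysis:

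- Age-group (under vs. over 60) and sex are fixed factors in every Experiment 2 model, whatever their p-values.
- The univariate gate for these two factors is deleted for Experiment 2.
- Age-group-by-consistency is included, as the standard term of the between-within model that the plan already describes.
- Continuous age is reported only as a labelled sensitivity analysis.

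This rewrites two sentences and changes no recruitment, procedure or data collection. It costs one degree of freedom each for age-group and sex out of 80 participants. The interaction takes 4 within-participant degrees of freedom with five consistency levels (5 − 1), or 8 if the nine stimuli are modelled separately (9 − 1). There is no other cost of substance.

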For Experiment 4, **our main hypothesis is that liquids with similar flow properties based on the IDDSI gravity-flow tests will elicit different tongue pressure and sEMG measures based on their actual viscosities.** This hypothesis is predicated on the idea that healthy adults modulate oral phase propulsive forces used for boluses of differing consistency with the goal of establishing uniform pharyngeal flow (as hypothesized for Experiment 2). Significant contrasts are expected between the two extremes of the liquid continuum: [*thin* and *slightly-thick*] vs. [*moderately-* and *extremely-thick*]. We expect that measures for the *mildly-thick* liquids will fall in between, but that differences may not be large enough to achieve statistical significance versus the extremes in pairwise comparisons. We predict that barium stimuli will elicit higher amplitudes of tongue-pressure than non-barium stimuli based on their increased density.

Experiment 6 is exploratory, with the goal of identifying differences in the following measures across stimuli:

- Oral processing time
- Number of chewing cycles
- Chewing duration
- Chewing force
- Bolus characteristics after chewing (photographs of the chewed bolus for measurement of particle size, and tests of bolus consistency using the IDDSI testing methods)
- Bolus flow measures (as described above for experiment 2)

The planned analyses will begin with univariate analyses of the effects of participant factors (sex, height, jaw length, neck length, neck circumference, number of occlusal pairs of teeth) on the physiological parameters of interest (chewing force, number of chewing cycles, chewing time, oral processing time). Any participant-level factors that are found to be significant will then be carried forward as covariates into linear mixed model ANOVAs with repeated measures, exploring relationships between the physiological parameters of interest and the dependent variables of interest (bolus particle size at the end of chewing and swallowing parameters as outlined for experiment 2). The results of these preliminary analyses for experiment 6 will inform the design of future experiments.

5. Risks and Benefits

Risks

The following risks will be disclosed to all participants in Experiments 2 and 4 prior to obtaining their consent to participate:

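### Experiment 2 hypothesises similar pharyngeal flow, but the plan only tests for differences, sets no similarity margin or decision rule, and does not specify how thickener is handled

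*Combined protocol and SAP*

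**What the plan says.** Section 4, Data Analysis, states for Experiment 2 that "our main hypothesis is that liquids with similar gravity-flow properties will show similar pharyngeal bolus flow". It then predicts that participants will adjust propulsion for starch-thickened stimuli, "achieving a similar outcome for both starch- and gum-thickened liquids in terms of pharyngeal bolus flow". Both statements claim similarity.

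The statistical goal in the same paragraph is different: "Our goal will be to detect differences in bolus flow measures" of at least 200 ms as a function of consistency, with Cohen's d of at least 0.5. On method the section says "The analysis will involve linear mixed model ANOVAs with repeated measures". Age group is the between-participants factor, and "bolus consistency will be used as the within-participants factor". The flow measures named are "the interval from the bolus passing the mandibular ramus until laryngeal vestibule closure; pharyngeal transit time".

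Section 3 describes the stimuli: "we will prepare starch- and gum-thickened liquids in 5 consistencies". Section 4, Data Collection Procedures, gives three boluses of each of nine barium stimuli in Experiment 2 but does not list the nine.

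Nowhere do the documents give a similarity margin, an equivalence test, a confidence-interval criterion or a reading for a non-significant result. No thickener term or starch-gum contrast is named.

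**The concern.** A difference test takes equality as its null hypothesis. Failing to reject it is not evidence for it, and rejecting it does not mean that the difference is large enough to matter. When the main hypothesis is similarity, the conclusion needs a limit that defines similar and a rule for comparing the estimate with that limit. The plan has neither, so two analysts with the same data could reach opposite conclusions on the main hypothesis and both claim to have followed the plan.

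A second gap is less certain. The text does not say whether the within-participants factor distinguishes starch from gum. If it is coded as IDDSI level, the model averages over thickener and the starch-gum part of the hypothesis is never estimated. If it is coded as nine stimuli, the contrast can be formed, but it is not named.

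**Working it through.** **The plan's own sample-size figure.** The plan states 36 per group for 80% power at alpha 0.05, and 40 enrolled (36/0.9 = 40, consistent with 10% attrition). With d = 0.5 and two-sided testing, a paired t-test needs 34 and a two-sample t-test needs 64 per group. The plan gives no SD and does not make clear which difference was powered, so 36 can be neither firmly reproduced nor refuted. This does not affect what follows.

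**Inputs.**
- n = 72, both age groups pooled (2 × 36).
- SD of 400 ms, inferred as 200 ms / 0.5. The documents state no flow SD.
- SD of the starch-minus-gum difference, if 400 ms describes participant-level values: 400 × √(2(1 − ρ)). This gives 283, 400 and 566 ms at assumed within-person correlations ρ of 0.75, 0.5 and 0.
- SD of that difference, if 400 ms is per bolus, three boluses are averaged and there is no participant-by-stimulus variance: 400 × √(2(1 − ρ)/3). This gives 163, 231 and 327 ms.
- Limit of ±200 ms, borrowed for illustration. The plan uses 200 ms only as a difference to detect between consistencies.

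**Significant yet inside the limit (true difference 100 ms).** At SD 400 the standard error is 400/√72 = 47.1 ms.
- Significance at two-sided 5% needs an estimate beyond about 1.994 × 47.1 = 94 ms.
- A 90% CI inside ±200 ms needs an estimate within about 200 − 1.667 × 47.1 = 121 ms.
- Estimates between 94 and 121 ms satisfy both. By normal approximation the probability is Φ((121.4 − 100)/47.1) − Φ((94.0 − 100)/47.1) ≈ 0.675 − 0.449 ≈ 0.23. Simulation also gives 23%.

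| SD of differences (ms) | Significant and inside ±200 ms |
|---|---|
| 163 | over 99% |
| 231 | 93% |
| 283 | 75% |
| 327 | 55% |
| 400 | 23% |
| 566 | under 1% |

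**Non-significant although the difference equals the limit.** A true 200 ms difference is non-significant in 1.3% of studies at SD 400, 16% at SD 566 and under 0.1% at SD 283 or in any of the per-bolus cases. With a limit of 100 ms, which is not in the documents, a true 100 ms difference would be non-significant 45% of the time at SD 400; two one-sided tests would pass it at most 5% of the time.

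**Power of an interval rule (true difference 0, one starch-gum pair, SD 400).** By normal approximation, power is about 2Φ(margin/47.1 − 1.667) − 1. The exact t-based values are 99% for ±200 ms, 87% for ±150 ms and 35% for ±100 ms. At SD 566 and ±200 ms, power is 82%.

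**The case against.** **The 200 ms figure already serves as the margin.** It is the only flow threshold in the plan and a reasonable candidate. But the text uses it as a difference to detect between consistencies, not as a limit for starch against gum at one level, and no rule applies it to an interval.

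**Thickener is covered.** Nine stimuli would fit thin plus four thickened levels by two thickeners, and the first step of the stepwise analysis is described as running across stimuli. This objection stands in part. A reader might infer that the model leaves thickener out. The documents do not show that: they leave the coding open, and the defect is that it is not specified.

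**The error rate is small.** This also stands at the documented threshold. A reader might infer that the plan carries a high risk of declaring false similarity. With a 200 ms limit that risk is at most 16% under the assumptions above and usually far lower. The larger figures need a tighter limit that the plan does not contain.

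**A tempting extra citation.** The Experiment 4 text has healthy adults modulating propulsion "with the goal of establishing uniform pharyngeal flow (as hypothesized for Experiment 2"), which might be read as restating the starch-gum hypothesis. That sentence concerns boluses of differing consistency, not two thickeners at one level, so it is not support for this point.

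**Equivalence testing is one preference among several.** True. Any margin fixed in advance, with estimates and intervals read against it, would close the gap.

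**Conclusion.** The concern holds and should be fixed. As written, the analysis cannot support Experiment 2's main hypothesis, because it yields only tests of difference and the plan sets no margin or rule for concluding similarity. This follows from the text and needs no assumed number. The point about thickener is weaker: its handling is unspecified, and whether the starch-gum comparison is tested depends on a coding choice that the documents do not state.

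The harm is an unsupported or contradictory conclusion, not a demonstrated high error rate. Its size cannot be fixed from the documents. The 23% conflict figure rests on an SD of differences of 400 ms, 72 participants and a borrowed 200 ms limit, and the range from under 1% to over 99% shows how strongly it depends on the SD.

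**What to change.** Before any starch-gum comparison is run:

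1. List the nine stimuli. Make the starch-minus-gum difference within each thickened level an explicit contrast, either with stimulus as the within-participants factor or by adding thickener and its interaction with IDDSI level. Do this for the flow measures named in Data Analysis.
2. Fix and justify a similarity margin without reference to the starch-gum results. The plan's 200 ms is a candidate.
3. Conclude similarity at a level only if the confidence interval of its contrast lies inside the margin, for example the 90% CI, which corresponds to two one-sided 5% tests. Keep difference tests for contrasts between consistency levels.

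The cost is in timing and in what can be claimed; no new participants or data are needed. The Participants section reports one age group complete and the other 90% complete, so the margin would be set late and its independence from the results should be documented. Similarity cannot be claimed where the interval is wide.

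Repeat boluses of one stimulus are not enough to check the margin's power, because they omit participant-by-stimulus variance. For example, in the per-bolus case with ρ = 0.5, an assumed interaction SD of 200 ms per stimulus raises the SD of differences from 231 to √(231² + 2 × 200²) ≈ 365 ms. Power for ±100 ms then falls from 95% to 49%.

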- b) During the intake process, we will ask to review a list of conditions that could alter the results of the research study and identify whether any of these conditions apply. The disclosure of any medications that they are currently taking, allows us to control for the possible influence of medication on oral sensory and motor function. Medications do not qualify as the basis for exclusion. However, it is important for us to collect information regarding the use of benzodiazepines and neuroleptic medications that are known to have possible effects on swallowing, particularly with respect to causing xerostomia (dry mouth).

Data Collection Procedures:

Experiment 2: Prior to data collection, a nasal cannula will be placed around the participant's head with flexible prongs resting in their nostrils to measure airflow.

A single use disposable tongue bulb for the hand-held Iowa Oral Performance Instrument (IOPI) will be placed inside the participant's mouth. Tongue pressure signal will be collected at the anterior position during 3 anterior maximum presses and 3 saliva swallows.

[figure not shown]

Image 1. Tongue pressure sensors.

Following sensor attachment, the participants will be seated on a chair inside the fluoroscopy unit. The videofluoroscopy recordings of swallowing involve a pulse rate of 30 pulses per second and video capture at 30 frames per second. The video output line from the fluoroscopy unit and the nasal cannula will then be connected to the KayPENTAX Digital Swallow Workstation Swallowing Signals Lab equipment, which is located on a properly insulated cart with an uninterrupted power supply and isolation transformer.

Participants will be asked to swallow 27 boluses (i.e., 3 boluses each of 9 different barium stimuli) in videofluoroscopy, with concurrent measurement of nasal airflow. All barium stimuli in Experiment 2 will be prepared using E-Z-Paque® powdered barium, in a 20% w/v concentration. Videofluoroscopy will be performed at maximum temporal resolution (30 pulses/second) and captured at 30 frames/second. The order of stimulus presentation will follow a randomized block design. Participants will be allowed to take natural sized sips of each stimulus from cups containing 40 ml. Cup weights before and after each sip will be taken on a digital balance so that sip volume and mass can be calculated.

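### The force-compensation hypothesis placed under Experiment 2 has no force data in Experiment 2, and its likely source, Experiment 4, was terminated without the analysis text being revised

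*Combined protocol and SAP*

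**What the plan says.** All references are to the combined protocol and SAP, section 4, Methods.

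- **Hypothesis (Data Analysis, Experiment 2 paragraph).** After the main hypothesis on pharyngeal flow, the plan predicts that participants "will use higher amplitudes of tongue pressure and/or submental muscle contraction (sEMG) during oral propulsion of starch-thickened stimuli". The same sentence then names the result that this extra force is supposed to bring about: "thereby achieving a similar outcome for both starch- and gum-thickened liquids in terms of pharyngeal bolus flow".
- **Measurements (Data Collection Procedures, Experiment 2).** "Tongue pressure signal will be collected at the anterior position during 3 anterior maximum presses and 3 saliva swallows". For the swallows under x-ray, "The video output line from the fluoroscopy unit and the nasal cannula will then be connected to the KayPENTAX Digital Swallow Workstation". The boluses are taken "in videofluoroscopy, with concurrent measurement of nasal airflow".
- **Sample (Participants).** Experiments 2 and 4 share one sample, planned as 40 adults under 60 and 40 over 60.
- **Experiment 4.** Participants and Data Collection Procedures both record that it was terminated on July 24 2018 because of an equipment fault, and no procedures for it remain. Data Analysis still gives its main hypothesis, on tongue pressure and sEMG, and says "This sample size will also be adequately powered for Experiment 4 to detect differences" of at least 10 mm Hg in tongue pressure.

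**The concern.** The hypothesis has two linked parts: participants push harder on starch-thickened liquids, and because they do, flow matches that of gum-thickened liquids. Experiment 2 can address the second part with its videofluoroscopic timings. It has no data on the first, because force is not recorded while the thickened liquids are swallowed.

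The plan's own wording joins the two parts causally. If flow proves similar, the result could be reported as support for compensation although no force was measured in those swallows. Section 1 gives the project's objective as learning how consistency and swallowing forces act together on bolus movement, so the mechanism matters to interpretation.

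A reader also cannot tell whether Experiment 4 yielded usable force data before it stopped, from how many participants, or whether those data will be analysed alongside Experiment 2.

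**Working it through.** The question is which signals exist for which swallows, so it is settled mainly by setting the sections side by side.

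**1. Force signals during the Experiment 2 boluses.** Three boluses of each of nine stimuli give 3 × 9 = 27 boluses per participant.

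| Signal in Experiment 2 | When recorded | Boluses covered |
|---|---|---|
| Videofluoroscopy | during boluses | 27 of 27 |
| Nasal airflow | during boluses | 27 of 27 |
| Tongue pressure | 3 maximum presses, 3 saliva swallows | 0 of 27 |
| Submental sEMG | not described | 0 of 27 |

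Presses and saliva swallows involve no thickened liquid. They can describe a participant's strength, but they cannot show a starch-versus-gum difference.

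**2. Could another described source fill the gap?**
- Data Processing says the collected signals may include tongue pressure and sEMG. That list is common to all experiments, and the only muscle it names is the masseter.
- The only sEMG placement in the procedures is over the masseter, in Experiment 6. Session 6-2 lists the sEMG sensors among the connections to the workstation; the matching Experiment 2 text does not.
- Experiment 6 uses different participants, and its procedures describe no starch-versus-gum comparison.
- Submental muscle is mentioned only in the hypothesis.

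**3. Where was force meant to come from?** The plural in "the healthy participants in these experiments", the shared sample, and the Experiment 4 hypothesis, which refers back to the uniform flow hypothesised for Experiment 2, all point to Experiment 4. The design divided the question: flow in Experiment 2, force in Experiment 4.

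**4. What remains of Experiment 4?** The termination is dated and explained. The documents do not give the number who completed it, the status of their data, or any link to Experiment 2.

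**5. The plan's sample-size figures.** The plan states 36 per group, raised to 40 for attrition. An allowance of 10% (my assumption; the plan gives no rate) reproduces this: 36 / (1 − 0.10) = 40, and 2 × 40 = 80. The 36 itself cannot be re-run because no SD or test is given. Power for 10 mm Hg in Experiment 4 cannot be computed either, because neither the SD nor the number with data is stated. The present point depends on none of these figures.

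**The case against.** The strongest reply is that the plan never asked Experiment 2 to measure force. The sentence speaks of more than one experiment, the sample is shared, and tongue pressure and sEMG form Experiment 4's own main hypothesis. The declared Experiment 2 target, differences of 200 ms or more, concerns bolus flow. The termination is openly recorded twice, and the adequacy sentence can be read as planning text about the intended 40 per group. This reply largely stands on intent. It does not remove the gap: once Experiment 4 stopped, the hypothesis lost its described source of data, and Data Analysis was not brought into line.

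Four stronger readings are tempting and are not supported.

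- **That the main Experiment 2 hypothesis is compromised.** It concerns flow, which is measured in all 27 boluses.
- **That Experiment 4 is under-powered.** If the 90% completion reported for the older group counts participants, that group holds 0.90 × 40 = 36, which equals the stated requirement of 36. How many of them did Experiment 4 is unknown, so neither adequacy nor inadequacy can be shown.
- **That the first modelling step cannot be run.** The plan speaks of "first identifying relevant influences of tongue-pressure and nasal airflow patterns across stimuli". That paragraph is general and also covers chewing. The phrase about stimuli may attach to nasal airflow alone, and participant-level tongue pressure is available. The sentence is ambiguous, not contradictory.
- **That the hypothesis should be deleted.** With recruitment of the younger group complete and the older group at 90%, keeping it and explaining why it cannot be tested is more transparent.

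**Conclusion.** The point holds as a mismatch between the analysis text and the data that the study as described can supply. In Experiment 2, force is recorded in 0 of 27 boluses per participant, so the compensation hypothesis cannot be tested there. Experiment 4 is the evident intended source, and the plan does not say whether it can still serve. The sentence on adequacy for Experiment 4 described a planned sample and should not stand as a property of the study as run.

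This deserves correction because the causal wording invites a conclusion that the data cannot carry. It does not threaten the main flow analysis. The conclusion assumes that the published Experiment 2 procedures are complete, meaning that no tongue-pressure or sEMG recording was made during boluses without being described. The number with Experiment 4 data is unknown, and nothing here depends on a value for it.

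**What to change.** 1. Keep the compensation hypothesis on record, but state that it cannot be tested from Experiment 2 because Experiment 4 was terminated.
2. State that similar flow for starch- and gum-thickened liquids in Experiment 2 will not be interpreted as evidence of greater tongue pressure or submental contraction.
3. If usable Experiment 4 data from before termination exist, name them as the source, give the number reached in each age group, and analyse tongue pressure and sEMG as outcomes (starch versus gum), labelled exploratory. If none exist, say so.
4. Keep the planned 40 per group as design rationale. Add that the Experiment 4 adequacy statement applied to that planned sample and no longer describes the study, and give the number actually reached.

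The cost is revised protocol and SAP wording, with no new data and no burden on participants. The downside is that the mechanism claim is given up, or limited to the participants with Experiment 4 data.
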